### Specific aims

1. To assess the preliminary impact of a SA intervention on outcomes that may be implemented in future studies, by assessing differences in the following between a SA intervention and unaffirmed standard SA control group of HBOC genetic counseling clients:
  - a. Intentions to talk with family, test uptake
  - b. Empowerment, decision self-efficacy
  - c. HBOC knowledge
2. To describe genetic counselors' (GCs) and clients' response to a novel, client-based SA intervention, including perceived impact, barriers, and facilitators to implementing such an intervention on a wider scale

3. To assess the percentage of eligible clients that completed a pre-visit SA intervention and if the SA intervention is effective in affirming clients.

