Appendix C) (Creswell et al., 2013; Havranek et al., 2012). They will then be asked to write about the item that is most important to them and why it may be important to them. The control group will rank the same list and be asked to write about the 9th ranked item and why it might be important to someone else. The control condition is consistent with the control used in other SA intervention studies. The 9th ranked item is chosen to inhibit a reverse effect where participants feel affirmed because they do not value something that is aversive to them. Both the intervention and control group will receive a 6-question survey of state anxiety along with the writing prompt, which will be used as a control measure.

Potential participants will be identified through the patient schedule and will be contacted by the student assistant investigator (AI), [name], about one week prior to their appointment to invite them to participate in the study and obtain verbal informed consent. Participants will be recommended to arrive 15 minutes prior to their scheduled appointment. When clients arrive at the HBOC clinic, the front desk staff will give client participants the SA or control intervention based on random assignment. The affirmation intervention or control condition will be completed directly before the regularly scheduled appointment.

Genetic counselors will be blinded to the study condition of their clients, although clients might choose to discuss the content of the intervention survey with the counselor. Counseling sessions will otherwise proceed according to protocol for the clinic. Clients will receive a paper survey as they leave the appointment regarding their demographic information (age, sex, education, race, ethnicity, cancer status) experience in the study, decision self-efficacy, empowerment, genetic knowledge, intentions to talk with family, information seeking, and intentions to pursue genetic testing if it was offered. They will be given the option to fill out the paper version or to access an electronic version online. Hard copy surveys will be returned to the front desk or by mail to the AI. Electronic versions will be sent to an email address provided by the client. A week after their appointment, all clients will receive an electronic reminder notification to complete the questionnaire. Upon completion of the online survey or paper questionnaire participants will be mailed a \$15 gift card.

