This aim will be analyzed as percent of yes/no response to intervention survey questions for both clients and counselors. There will also be open ended questions for specific impacts, barriers, and facilitators to be mentioned, which will be analyzed using thematic analysis of answers. The AI will create a codebook based on initial read through and subsequently code all answers. A separate coder will validate ten percent of answers for consistency.

Aim 3: To assess the percentage of clients that completed a pre-visit SA intervention among client participants and if the SA intervention is affective in affirming clients.

Intervention uptake will be reported as a percentage of participants who were eligible based on counselor referral and who were contacted by AI that completed the SA intervention and client survey. Effectiveness of affirmation is an internal control and will be assessed by screening the last question on the intervention for those in the intervention group who report higher than a 2 and those in the control group who report lower than a 5. Additionally, transcripts of intervention essays will be analyzed for affirmation themes.

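### Aim 3 lists affirmation themes in the essays as a check on whether self-affirmation (SA) affirms clients, but the prompts assign that content by arm, so themes mainly show adherence to the prompt.

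*Combined protocol and SAP*

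**What the plan says.** Under Specific aims, Aim 3 includes the question "if the SA intervention is effective in affirming clients"; section 7.0 restates it as "if the SA intervention is affective in affirming clients". The analysis text for that aim names two sources of evidence.

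- Self-report comes first: "Effectiveness of affirmation is an internal control and will be assessed by screening the last question on the intervention". The screen picks out "those in the intervention group who report higher than a 2 and those in the control group who report lower than a 5".
- The essays come second: "Additionally, transcripts of intervention essays will be analyzed for affirmation themes". No other purpose is given for them.

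The writing task is described in section 5.0 and again under Intervention. Both arms rank the same 11 values. Of SA clients the protocol says: "They will then be asked to write about the item that is most important to them and why it may be important to them". Controls write about their ninth "ranked item and why it might be important to someone else".

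The plan does not define an affirmation theme, say which arms' essays are read, mention masking of coders, or say what finding would count against affirmation. The codebook and the 10% second-coder check are described only for the open-ended answers of Aim 2.

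**The concern.** Section 1.0 describes the target of the task as a psychological state: a reinforced sense of personal adequacy. Essay content is not a measure of that state. In the SA arm, writing about a personal value is the assignment; in the control arm, the assignment points away from the self. A client whose self-integrity did not move at all would still produce the theme if she did as she was asked.

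Two things are at stake. First, if themes are reported as support for effectiveness, Aim 3 gains a line of evidence that separates a working task from an inert one only poorly. Second, what the essays can show well has no stated place in the plan: how many SA clients did the task as instructed, and how many controls wrote about their own values anyway. The second matters because section 5.0 explains that the ninth-ranked item was chosen to avoid controls feeling affirmed. If controls do affirm themselves, the arm differences that Aim 1 uses to choose outcomes and size the next study will tend to shrink.

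**Working it through.** The plan attaches no figure to the essay analysis, so there is nothing to reproduce. The check has two parts.

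**1. The passages side by side**

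| Element | SA arm | Control arm |
|---|---|---|
| Item written about (section 5.0) | ranked first by the client | ranked ninth by the client |
| Whose reasons | her own | someone else's |
| Content if the prompt is followed | own value affirmed | own value not affirmed |
| State measured by the essay | none | none |

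If only SA essays are read, there is no comparator. If both arms are read, the contrast contains the difference between the two prompts, and any effect on the client cannot be separated from it.

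**2. Illustration of size**

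Input from the documents: 35 clients per arm (section 5.0). Assumptions of this check, none of them in the plan:

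- the task has no effect on the client's state;
- themes follow the prompt, so a share c of SA essays and a share 1 − c of control essays carry them;
- a result counts as positive if a majority of SA essays (18 or more of 35) carry the theme or, alternatively, if a two-sided Fisher exact test gives p < 0.05 with SA above control.

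With X ~ Bin(35, c) for SA and Y ~ Bin(35, 1 − c) for control, the majority criterion is P(X ≥ 18). The Fisher criterion is the sum of P(X = x)·P(Y = y) over all pairs with x > y and p < 0.05.

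| c | Expected SA essays with theme (35 × c) | P(majority of SA essays) | P(Fisher significant) |
|---|---|---|---|
| 0.6 | 21 | 0.886 | 0.28 |
| 0.7 | 24.5 | 0.994 | 0.88 |
| 0.8 | 28 | >0.999 | 0.999 |
| 0.9 | 31.5 | >0.999 | >0.999 |

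The control rate need not be 1 − c. If 70% of SA and 50% of control essays carry the theme, the Fisher probability is about 0.31; for 80% against 60% it is about 0.36. So the SA-only reading is nearly sure to look favourable at 70% compliance or more, while the between-arm reading depends strongly on the assumed rates.

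**The case against.** The strongest reply is that the plan does not use the essays as proof. They are introduced as an addition to the self-report question, with no count, threshold, test or weighting. Effectiveness of affirmation is called an internal control, which is the language of a manipulation check. Where effectiveness enters Aim 1 as a covariate, section 7.0 ties it to a last question on a form, never to the essays. All of this stands. A reader might infer that the plan is bound to declare the task effective, or that essay themes could override a flat self-report result. The documents support neither: they contain no rule from which such a verdict could follow.

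It can also be said that the intervention essays may mean those of both arms. Section 5.0 uses the word intervention for the control form too, and the self-report screen covers both groups. That is a fair reading, and under it self-affirming control essays could come to light. The plan still does not say which arms are read or what is done with the result.

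Finally, a prompt fixes a topic, not every feature of the writing. A codebook that looked for expressed personal adequacy beyond the assigned topic would be less circular. That is true, but no such definition is given. The illustration scores topic alone, so part of its result is built into its assumption.

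What remains is that the only stated purpose of the essay analysis is to help answer whether SA affirms clients, and that the prompts supply most of the content being sought.

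**Conclusion.** The point holds in a limited form. Affirmation themes in these essays mainly reflect adherence to the assigned prompt and are weak evidence that self-integrity changed. It would go too far to say that this evidence comes out positive whatever happens: that needs a decision rule the plan does not have, high compliance, and coding by topic alone. The probabilities above are illustrative, and on the between-arm criterion they run from 28% to above 99.9% across the assumed rates.

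The consequence is confined to what Aim 3 may conclude and to the reading of the Aim 1 effect sizes. No Aim 1 estimate takes the essays as input, and the sample size is unaffected. The self-report question is the first-named check, and this argument does not undermine it. However, Appendix C is not in the supplied text, so the wording and scale direction of that question could not be examined. This is a worthwhile, inexpensive improvement to a supplementary analysis.

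**What to change.** In section 7.0, Aim 3:

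- Designate the essay coding as a measure of fidelity and contamination, not of effectiveness.
- State that the essays of both arms are coded with one prespecified codebook, from transcripts with the prompt and arm label removed as far as possible.
- Report, each with a 95% confidence interval, the percentage of SA essays that follow the prompt and the percentage of control essays that affirm the writer's own values.
- Base any statement that SA affirms clients on a between-arm comparison of the self-report question, in place of the separate cut-offs within each arm. First confirm from Appendix C that the question asks about the client's state after writing and does not merely reflect the prompt she was given.
- Use the control-essay percentage when interpreting the Aim 1 effect sizes. It shows possible contamination; by the same reasoning as above, it does not prove that those controls were affirmed.

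The cost is a change of wording, plus coding of up to 35 short control essays if they were not already to be coded. The essays are produced by the study in any case, so client burden and sample size do not change. Aim 3 loses one apparently supportive line of evidence, and masking will be imperfect because the text of an essay often reveals its prompt.

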## **8.0 Description of potential benefits of study:**

### **8.1 Direct benefits to participants**

There are minimal direct benefits to participants. Client participants in the intervention group may benefit from a richer counseling experience through greater openness and exploration of values if the intervention is successful.

### **8.2 Collateral benefit to participants**

A collateral benefit that could result from this study is that those in the self-affirmation group may be more likely to spontaneously self-affirm in future situations after engaging in the SA measure (Brady et al, 2016).

### **8.3 Benefits to society**

This study could benefit society by building on our knowledge about which outcomes are subject to SA. It could also enlighten counselors on ways to engage clients in a genetic counseling session. Furthermore, the feasibility study can give information about possible barriers to other similar interventions delivered prior to a genetic counseling visit.

## **9.0 Description of likelihood and seriousness of harms and how safety will be maximized:**

This study is unlikely to cause serious harms. There is small chance that there could be low level psychological harm caused by this study because SA has been shown to increase openness to a threatening message and therefore increase feelings of vulnerability and possibly anxiety (Klein et al., 2011). While this may occur among participants in the intervention arm, the magnitude of the risk is likely small and will be mitigated by the fact that they will be seen by genetic counselors who have training to manage clients' anxiety. There also could be benefit to increasing anxiety in a situation where action needs to be taken to avoid a threat, such as continuing recommended screening for early detection of breast cancer. There is no increased risk to pregnant women or fetus related to this study protocol.

9.1 Therapeutic interventions *N/A*

9.2 Diagnostic interventions *N/A*

9.3 Radiation *N/A*

9.4 Sedation *N/A*

9.5 Risks to family relationships and other psychosocial or economic harms *N/A*

## 10.0 Description of how privacy and confidentiality of medical information/biological specimens will be maximized

Code words will be used to coordinate assembly of study documents and identifiable client information will not be connected with study documents. For initial surveys to be matched with post-session surveys for later analysis, clients will choose a code word compiled by asking: What is the first street that you lived on? What was your first pet's name? (e.g. OakMondo). This code word will be put on all documents relating to a given participant. The client will tell the counselor the code word during the appointment in order to label the counselors' post-visit survey, but no record of the code word in association with the client's name will be created. Cancer is a common condition and we do not expect clients to be identifiable through their diagnosis. Code words will be destroyed at completion of the study.

Genetic counselor surveys will not include identifying information for the counselor or which after-visit survey was conducted by each counselor. After-visit genetic counselor surveys will include the client code-word that will aid in confirming that surveys are being completed by counselors.

10.1 Description of any clinical/demographic information that will be included.

For clients, demographic information will be collected including: education, age, sex, race, and clinic site. No demographic information will be collected for counselors.

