#### **5.0 Description of procedures:**

In this intervention-based randomized controlled feasibility study, Hereditary Breast and Ovarian Cancer (HBOC) genetic counseling clients will receive an intervention and short survey before their appointment and will complete a survey after their appointment. Genetic counselors who counsel participating clients will complete a post-appointment survey after each appointment with a participating client and a survey at the end of the study.

Thirty-five client participants will be randomly assigned to complete the self-affirmation intervention and 35 participants will complete the control condition. Client participants will be patients being seen for an initial appointment for genetic counseling at the HBOC genetic counseling clinic, regardless of current cancer status. All client participants will take a state anxiety measure before their appointment to control for some of the variability in indication. Client participants will also indicate if they have cancer, if they have received genetic testing, and if they were offered genetic testing at the current visit. Genetic counseling can be indicated for patients without cancer who have a family history of cancer, for patients with cancer, and for self-referred patients who are concerned about their cancer risk. Most often, the initial cancer genetic counseling appointment occurs before qualification for genetic testing is assessed and clients have a follow-up appointment to receive results. Sometimes oncologists or primary care physicians order genetic tests and the initial genetic counseling appointment includes results delivery and education. Any client with an initial genetic counseling appointment will be invited to participate in the study. Follow-up appointments will not be included because patients already have a relationship with the genetic counselor. The four genetic counselors, who have appointments with the participating clients, will be enrolled in the study as genetic counselor participants.

The SA intervention consists of participants ranking 11 items (artistic skills, athletics, business/money, creativity, independence, music, politics, relationships with friends and family, religious values, sense of humor, spontaneity) from most important to least important (See

[figure not shown]

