### **Counselor after visit survey (Appendix E)**

The counselor after visit survey consists of a counselor version of the Genetic Counseling Outcome Scale (GCOS-24). This scale was modified from the original GCOS-24 for use by counselors and parallels the client version. This measure consists of 24 likert scale questions that assess counselor's perceptions of the client's empowerment. It should take 3-5 minutes for the counselors to complete after each session.

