### 6.5 Description of criteria for withdrawal from study.

Client participants may withdraw from the study at any time during or immediately following completion. While completing the survey, the participant may choose not to answer any particular question. Surveys will be anonymous, using a code word to coordinate documents (see Section 10) and never linked to contact information. If client participants request to withdraw from the study if they must provide their code word to identify and remove their documents.

Genetic counselor participants may with withdraw from the study at any time during the study. If genetic counselor participants withdraw any previous surveys will be included in the analysis but future patients will not be consented to participate. Surveys will not be linked to the individual counselor.

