## **7.0 Description of study statistical considerations and/or analytic plan:**

*Aims have been copied here for ease of interpretation.*

Aim 1: To assess the preliminary impact of a novel SA intervention on outcomes that may be targeted in future studies, by assessing differences in the following between a SA intervention and unaffirmed standard SA intervention control group of HBOC genetic counseling clients:

- a. Intentions to talk with family, test uptake
- b. Empowerment, decision self-efficacy
- c. HBOC knowledge

The primary goal of analysis of aim 1 is to identify which outcomes would be most appropriate for follow up studies and the necessary sample size for adequate statistical power.

For decision efficacy, the scores on the Decision Self-Efficacy Scale (See section 2 of client survey, Appendix D) will be compared between groups using linear regression controlling for education, race, anxiety score, and effectiveness of intervention (based on last question on intervention Appendix C). Intention to talk with family, genetic testing uptake, and information seeking will be measured similarly using linear regression.

Client empowerment will be analyzed by using the GCOS-24 a 24-item likert scale completed by clients and parallel scale by genetic counselors (See section 3 of client survey of appendix D and appendix F). Both scales will be compared between groups using linear regression controlling for education, race, anxiety score, and effectiveness of intervention (based on last question on survey). Discrepancies between counselor and client surveys will be analyzed using dyadic analyses. For this analysis, we will assess the correlation between paired client and genetic counselor GCOS-24 for the compete survey and for the individual questions.

HBOC knowledge will be analyzed between groups using linear regression testing the knowledge scale (See section 4 of client survey, Appendix D) and controlling for education, race, anxiety score, and effectiveness of intervention.

Effect sizes and standard deviations for each outcome will be identified, and an estimated sample size for a fully powered study will be estimated based on power calculations.

Aim 2: To describe genetic counselors' (GCs) and clients' response to a novel, client-based SA intervention, including perceived impact, barriers, and facilitators to implementing such an intervention on a wider scale

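### Four counselors supply the counselor-rated empowerment scores but the forms carry no rater label, so scoring severity can be separated from client differences only between sites, at a modest cost in precision and in the client-counselor correlation

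*Combined protocol and SAP*

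**What the plan says.** Section 5.0 sets the number of raters: "The four genetic counselors, who have appointments with the participating clients, will be enrolled in the study as genetic counselor participants". Section 6.1 places two of them at St. Luke's and two at Medstar. Each fills in a form after every study visit. The description of the counselor after-visit survey says: "This measure consists of 24 likert scale questions that assess counselor's perceptions of the client's empowerment".

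Two sections keep the rater off the form. Section 10.0: "Genetic counselor surveys will not include identifying information for the counselor or which after-visit survey was conducted by each counselor". Section 6.5: "Surveys will not be linked to the individual counselor". The only label is the client's code word.

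Section 7.0 uses the scores in two ways:

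- For the arm comparison of the client and counselor scales: "Both scales will be compared between groups using linear regression controlling for education, race, anxiety score, and effectiveness of intervention".
- For agreement between client and counselor: "we will assess the correlation between paired client and genetic counselor GCOS-24 for the compete survey and for the individual questions".

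Neither analysis has a counselor or site term. Section 10.1 does collect site for clients: "demographic information will be collected including: education, age, sex, race, and clinic site". Through the code word, site can be carried across to the matching counselor form.

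**The concern.** The counselor form asks for a judgment about someone else's empowerment, a construct that the protocol says includes emotional regulation and hope. Two counselors seeing the same client could well score such items differently. The documents do not say by how much, but where it happens the difference belongs to the rater and not to the client.

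With a rater label, that difference can be taken out. Without one, it enters the residual of the arm comparison and the spread of the paired scores. Section 7.0 says that Aim 1 exists to choose outcomes and a sample size for the next study from the effect sizes and standard deviations found here. Rater variance would be carried into those figures unseen, and a weak client-counselor correlation could mean real disagreement or merely different scoring habits. The label cannot be reconstructed once forms are returned.

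**Working it through.** **The plan's own figure.** The only sample size computed in the documents is 296 for a future study (section 6.1: d = 0.35, alpha 0.05, and 0.85 written as beta but read here as power). The normal approximation gives 147 per arm, 294 in total. The two-sided t-test gives 147.55, so 148 per arm and 296 in total. The figure reproduces, and the present point does not depend on it.

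**Inputs from the documents.** 70 clients, 35 per arm, with no stratification described (section 5.0); about 54 at St. Luke's and 16 at Medstar (section 5.0); two counselors per site (section 6.1); counselors blinded to arm (section 5.0).

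**Assumptions.** Caseload split equally within site (27, 27, 8, 8); share of score variance between raters (ICC) 0.05 to 0.30; true within-rater client-counselor correlation 0.50; true arm effect zero; other covariates left out. The documents give none of these.

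**How much site can recover.** Let w be each rater's share of clients. The expected between-rater variation in the sample is proportional to 1 − Σw² = 1 − 2(27/70)² − 2(8/70)² = 0.676. The part within sites is (54/70)(0.5) + (16/70)(0.5) = 0.5. So 0.5/0.676 = 74% lies between the two counselors at a site and is lost. Site can absorb the other 26%.

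**Simulation of the design (6,000 runs per row).** The SE is that of the arm difference, in SD units.

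| ICC | SE, no rater term | SE, site term | SE, rater term | Variance ratio, none vs rater | r pooled | r within site | r within rater |
|---|---|---|---|---|---|---|---|
| 0.05 | 0.2377 | 0.2383 | 0.2387 | 0.99 | 0.487 | 0.489 | 0.496 |
| 0.10 | 0.2374 | 0.2373 | 0.2339 | 1.03 | 0.480 | 0.484 | 0.497 |
| 0.20 | 0.2297 | 0.2267 | 0.2156 | 1.14 | 0.461 | 0.470 | 0.496 |
| 0.30 | 0.2283 | 0.2231 | 0.2059 | 1.23 | 0.443 | 0.456 | 0.497 |

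The variance ratio is the square of the SE ratio, for example (0.2283/0.2059)² = 1.23. The mean estimated arm difference was about zero in every row, with and without the rater term.

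**Hand check.** Without a rater term the expected residual variance is (1 − ICC) + ICC × 0.676 × 70/69. With one it is (1 − ICC), multiplied by about 69/66 for the three degrees of freedom spent.

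- ICC 0.10: 0.969/(0.900 × 1.045) = 1.03.
- ICC 0.30: 0.906/(0.700 × 1.045) = 1.24.

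Repeating the simulation gives 1.02 and 1.22 at the two ends. The three sets agree to within about 0.02.

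**Correlation.** The pooled value is 0.480/0.50 = 0.96 of the true one at ICC 0.10 and 0.443/0.50 = 0.89 at ICC 0.30. Centring by site alone raises the latter to 0.456/0.50 = 0.91.

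**The case against.** The best defence is that this is a small loss accepted for a good reason. Counselors are research participants. Each form is joined by code word to the client's own GCOS-24, a scale built to measure outcomes of genetic counseling, so a letter plus site would yield outcomes by nearly identifiable counselor. The counselor rating also supplements the client's own score, and section 3.0 says significant results are not expected from a feasibility study. All of that stands. It lowers the priority, but it does not make the pooled figures easier to interpret.

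Four stronger readings are tempting, and the documents do not support them.

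- *The arm comparison is biased.* Randomization and blinded counselors rule out systematic bias from severity. What remains is noise and chance imbalance.
- *Rater severity cannot be removed at all.* Site is collected, so about a quarter of it can be.
- *The variance is inflated by 1/(1 − ICC), that is 1.11 to 1.43 at ICC 0.10 to 0.30.* That holds only if the assumed share is the share realised among these four raters, and it ignores the degrees of freedom a rater term uses. Likewise, whether the total SD is wrong for planning depends on the next trial. If that trial also pools counselors without adjustment, the total SD is the right one.
- *Pooling manufactures agreement.* If 20% of counselor-score and 10% of client-score variance lay between counselors and were perfectly aligned, a correlation of √(0.2 × 0.1) = 0.14 would appear with no within-rater agreement. This is a worst case, and part of it could be real: one counselor's clients may truly be more empowered and be rated so. Pooled and within-rater correlations answer different questions.

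**Conclusion.** The point holds as a limitation worth correcting, not as a flaw that undermines the trial. The plan collects ratings from four people, deliberately records no rater, and analyses the scores with no rater or site term. For a between-rater share of 10% to 30%, the arm-effect variance is about 1.02 to 1.22 times what a rater term would give, and a true within-rater correlation of 0.50 falls to about 0.48 to 0.44. At a 5% share the rater term gains nothing for the arm comparison. The correlation is the stronger ground, because without a label nobody can tell scoring habit from disagreement. The sizes rest on the assumed shares, the assumed 0.50 and equal caseloads within site. The absence of the label and of the model terms rests on the text alone.

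**What to change.** **Forms.** Amend sections 6.5 and 10.0 so that each after-visit form completed from now on carries a neutral rater letter, A to D, with no key kept. Leave the end-of-study opinion survey unlabelled.

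**Analysis (section 7.0).** Add rater to the counselor GCOS-24 model. For forms without a letter, use clinic site. Section 6.1 shows that recruitment at St. Luke's is under way, so its existing forms would make one unlettered St. Luke's category beside the lettered ones. Report the client-counselor correlation within rater (one correlation of rater-centred scores, or site-centred where no letter exists) beside the pooled one, and say which is used for planning.

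**Cost.** One letter per form and short text changes. An amendment adding Medstar is already in hand (sections 6.1 and 14.6), so its two counselors could be lettered from their first form. There are three drawbacks. With two counselors per site a letter may be guessable. The confidentiality wording must change, as must the counselor consent if it repeats the promise. Forms already returned can be adjusted for site only. If the investigators judge the privacy cost too high, adding the site term and stating the limitation is the fallback.
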